8.3. Exploratory Efficacy Analysis

All exploratory endpoints will be summarized, and P values will be included for descriptive purposes only.

[figure not shown]
The following analyses will be performed on the observed data for the ITT Population. All derived variables will be computed as described in Section 6.1.7.

1. The PH94B and placebo proportions of PGI-C responders will be compared using a parallel analysis to that described for the CGI-I endpoint (Section 8.2.1).

5. Proportion of SUDS responders (subjects with a ≥20-point improvement in average SUDS score from Visit 2 [Baseline] to Visit 3 [Treatment]) will be compared between the PH94B and placebo arms using a normal approximation test for a difference in binomial using a parallel analysis to that described for the CGI-I endpoint (Section 8.2.1).

6.

The primary and secondary endpoints will be summarized by subgroups of interest

Racial categories will be combined into larger categories should there be fewer than 5 subjects in a particular category within a treatment arm. Analyses will be performed on the observed data.

Subgroup Analyses of Primary Efficacy Endpoint

The primary efficacy endpoint of change in average SUDS scores from Visit 2 (Baseline) to Visit 3 (Treatment) will be compared between PH94B- and placebo-treated subjects

Subgroup analyses of the primary efficacy endpoint will be analogous to the ANCOVA analysis outlined in Section 8.1.1 but imputation will not be performed.

Subgroup Analyses of Secondary Efficacy Endpoint

The secondary efficacy endpoint of proportion of CGI-I responders will be compared between PH94B- and placebo-treated subjects within each of the subgroups listed above. Subgroup analyses will be compared using a normal approximation (Wald) test for the difference between 2 binomial proportions as described in Section 8.2.1.

9. Safety and Tolerability Analysis

Safety in this study will be evaluated based on data collected on AEs, clinical laboratory assessments, vital signs, 12-lead ECGs, suicidality, level of depression, and physical examinations including examination of the nasal passages.

All safety analysis reporting will be based on the Safety Population (as defined in Section 5). No formal statistical testing will be conducted for the safety analyses. Descriptive statistics will be used to evaluate safety data. Summaries will present data by treatment group and overall subjects. Listings will list safety data by treatment group and subject.

9.1. Adverse Events

Treatment emergent AEs (TEAEs) are defined as:

- AEs with onset at the time of or following the start of treatment with IP through Visit 4 (Follow-Up) or
- AEs starting prior to the start of treatment with IP but increasing in severity or relationship at the time of, or following, the start of treatment with IP through Visit 4 (Follow-Up).

Any medical condition that is present at the time that the subject is screened will be considered as baseline and not reported as an AE. However, if the study subject's condition deteriorates at any time during the study, it will be recorded as an AE.

The Investigator will record all reportable events with start dates occurring any time after informed consent is obtained until 7 days after the last day of study participation. Events will be followed for outcome information until resolution or stabilization. Missing and partially missing start dates will be imputed for the purpose of analysis as described in Section 6.1.8.

All AEs, TEAEs, and serious AEs (SAEs) will be coded using the MedDRA dictionary, as discussed in Section 6.1.8.

All AE data will be summarized for 2 periods: before Visit 3 (Treatment) dosing and during or after Visit 3 (Treatment) dosing. The reporting is done in this manner due to the difference in study drug exposure during these 2 periods. All subjects will receive placebo at Visit 2 (Baseline), and all subjects will receive their randomized treatment at Visit 3 (Treatment). Thus, between Visit 2 (Baseline) up to dosing at Visit 3 (Treatment), subjects will have only been exposed to placebo. From Visit 3 (Treatment) dosing and onward, subjects will have been exposed to either active drug (PH94B) or placebo.

All AE data will be categorized as Severe > Moderate > Mild. Relationship of all AEs to IP will be categorized as related or not related. In the summaries showing severity and relationship to study drug, the event with the maximum severity or strongest relationship to study drug will be reported. For the purposes of analysis, if a particular event is missing the severity, it will be categorized as severe, and it if it missing the relationship, it will be categorized as related.

An overall summary of TEAEs will be provided; this will present number and percent of subjects who reported at least 1 of the following: TEAE (including any TEAE, TEAEs by maximum severity, and related TEAEs), TEAE leading to discontinuation of the study drug, TEAE leading to discontinuation from the study, serious TEAEs, and SAEs leading to death.

In addition to the overall summary, summaries of the number and percentage of subjects with TEAEs will be displayed for each treatment group by SOC and preferred term. Summaries of TEAEs by severity (Severe > Moderate > Mild) and relationship to IP (Related > Not Related) will also be provided. Serious TEAEs and TEAEs resulting in discontinuation of IP will be summarized separately in a similar manner.

Subject listings of AEs, SAEs, and AEs causing discontinuation of IP will be produced. Adverse events that are treatment emergent will be flagged.

The AE summary tables will include counts of subjects. Therefore, if a subject experiences more

than 1 episode of a particular AE, the subject will be counted only once for that event. If a subject has more than 1 AE that is coded to the same preferred term, the subject will be counted only once for that preferred term. Similarly, if a subject has more than 1 AE within an SOC, the subject will be counted only once in that SOC. This will be handled separately for each time period (Before Visit 3 Dosing and During or After Visit 3 Dosing).

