11.1. Definitions

11.1.1 Adverse Events

An AE is defined as any untoward medical occurrence in a patient or clinical investigation subject administered a pharmaceutical product that does not necessarily have a causal relationship with this treatment. An AE can therefore be any unfavorable and unintended sign (including an abnormal laboratory finding, for example), symptom, or disease temporally associated with the use of a medicinal product, whether or not related to the medicinal product.

Pre-existing diseases or conditions will not be considered AEs unless there is an increase in the frequency or severity, or a change in the quality, of the disease or condition. (Worsening of a pre-existing condition is considered an AE.)

In this study, AEs will be classified by time of occurrence and Visit 3 group assignment to more clearly identify those arising after exposure to placebo only and those arising after exposure to PH94B.

Pregnancy is not considered an AE, but it is an important medical event, which must be followed up as described in Section 11.3.1.

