11.1.5 Treatment-emergent Adverse Events

Treatment-emergent AEs are defined as:

- AEs with onset at the time of or following the start of treatment with IP through the Follow-up Visit or
- AEs starting prior to the start of treatment but increasing in severity or relationship at the time of, or following, the start of treatment with IP through the Follow-up Visit.

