11.2. Event Assessment and Follow-up of Adverse Events

The occurrence of an AE or SAE may come to the attention of study personnel during study visits and interviews of a study subject presenting for medical care, or upon review by a study monitor.

All AEs including local and systemic reactions not meeting the criteria for SAEs will be captured on the appropriate eCRF. Information to be collected includes event description, time of onset, clinician's assessment of severity, relationship to study product (assessed only by those with the training and authority to make a diagnosis), and time of resolution/stabilization of the event. All

Page 54 of 101

Amendment 3, Version 4.0

12-Aug-2022

AEs occurring while on study must be documented appropriately regardless of relationship. All AEs will be followed to adequate resolution.

Any medical condition that is present at the time that the subject is screened will be considered as baseline and not reported as an AE. However, if the study subject's condition deteriorates at any time during the study, it will be recorded as an AE.

Changes in the severity of an AE will be documented to allow an assessment of the duration of the event at each level of severity to be performed. AEs characterized as intermittent require documentation of onset and duration of each episode.

The Investigator will record all reportable events with start dates occurring any time after informed consent is obtained until 7 days after the last day of study participation. At each study visit, the investigator will inquire about the occurrence of AE/SAEs since the last visit. Events will be followed for outcome information until resolution or stabilization.

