6.1.1. Baseline

Baseline for each study assessment is defined in Table 2.

Table 2: Baseline Definitions

Parameter	Baseline
Safety Variables (clinical laboratory assessments, vital signs, ECGs, physical examinations)	The last non-missing assessment before the first dose of study drug given at Visit 2 (Baseline).
C-SSRS Scores	Scores on the Baseline version of the C-SSRS given at Visit 1 (Screening).

divided by the number of SUDS scores recorded during the speech performance.

Average Anticipatory SUDS Score

Sum of Visit 2 (Baseline) SUDS scores

divided by the number of recorded SUDS scores.

LSAS total score, HAM-D total score.

Total score at Visit 1 (Screening).

Abbreviations: CGI-I = Clinical Global Impression of Improvement; ECG = electrocardiogram; C-SSRS = Columbia-Suicide Severity Rating Scale; Scale; LSAS = Liebowitz Social Anxiety Scale; PGI-C= Patient Global Impression of Change; SUDS = Subjective Units of Distress Scale

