7.4. Exposure and Compliance

Drug and placebo will be supplied in identical

Each spray delivers 1.6 μg per 100 μL spray. At Visit 2 (Baseline) and Visit 3

(Treatment), site personnel will instruct the subject to self-administer the IP by 1 spray into each nostril (right and left nasal passages), for 2 total sprays per dose; thus, 1 dose equals 2 sprays, or 3.2 μg. All vials dispensed at Visit 2 (Baseline) will contain placebo nasal spray solution.

Total number of doses of placebo and PH94B will be summarized by treatment group and subjects, by study visit for the Safety Population. Data will also be presented in a by-subject listing.

8. Efficacy Analysis

All efficacy analyses will be performed on the ITT Population (as defined in Section 5) unless otherwise noted. The order of testing for the primary and secondary endpoints is discussed in Section 6.1.3. Exploratory endpoints are not included in the testing strategy.

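### SAP 9.1 ties treatment emergence only to the Visit 2 placebo dose, so an AE that worsens after the randomised Visit 3 dose may be tabulated in the placebo-only period

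*SAP*

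**What the plan says.** **Definition.** SAP 9.1 gives two routes to treatment emergence: onset at or after the start of investigational product, or "AEs starting prior to the start of treatment with IP but increasing in severity or relationship" at or after that start. Protocol 11.1.5 has the same second limb: "AEs starting prior to the start of treatment but increasing in severity or relationship at the time of", or after, the start of treatment.

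**First dose.** SAP Table 2 (Section 6.1.1) places the first dose at Visit 2, and SAP 7.4 says "All vials dispensed at Visit 2 (Baseline) will contain placebo nasal spray solution".

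**Periods.** SAP 9.1 states: "All AE data will be summarized for 2 periods: before Visit 3 (Treatment) dosing and during or after Visit 3 (Treatment) dosing". The reason it gives is that exposure differs: placebo only up to Visit 3 dosing, PH94B or placebo from then on.

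**Assignment to a period.** Protocol 11.1.1 says "AEs will be classified by time of occurrence and Visit 3 group assignment", and SAP Section 5 uses the same terms. Worsening is not mentioned as a ground for assignment.

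**Severity.** For the severity and relationship tables, SAP 9.1 says that "the event with the maximum severity or strongest relationship to study drug will be reported". It also says that the rule of counting a subject once is applied separately in each period.

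**Recording.** Protocol 11.2 says "Changes in the severity of an AE will be documented", so that duration at each severity level can be assessed. It does not say whether a change opens a new record or updates the existing one.

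**The concern.** The split at Visit 3 exists to separate placebo-only experience from experience after the randomised dose. The definition that feeds the tables has one clock, which starts at the Visit 2 placebo. An AE already present at Visit 3 that gets worse after the randomised dose is exactly what a worsening limb is meant to catch, and no limb is anchored there to catch it.

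Safety and tolerability compared with placebo is a stated objective, and incidence and severity of AEs is a stated endpoint. The comparison that answers it is the one after Visit 3 dosing. If worsenings drop out of that period, the comparison is blind to one form of drug effect, and the placebo-only period may show grades that were reached only later.

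**Working it through.** The plan states no figure on this point, so the check is a trace of the rules through three AE histories.

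**Step 1: the anchor.** First dose = Visit 2 (SAP Table 2); Visit 2 dose = placebo (SAP 7.4). SAP 9.1.1 tabulates treatment-emergent events in the *Before Visit 3 Dosing* period, which is possible only if the clock starts at Visit 2. Both limbs therefore run from the placebo dose.

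**Step 2: the likely period rule.** The documents classify by when an AE occurs and do not name onset as the period rule. Four things point to start date:
- Protocol 11.2.3 lists one start date (first occurrence), one stop date and one severity per AE, and no date of worsening.
- The AE date rules in SAP 6.1.8 impute start dates only.
- Protocol 13.1.5.1 speaks of events that arise following each exposure.
- SAP 6.1.8 has an explicit before/after Visit 3 rule for medications, with uncertain cases placed after dosing. AEs that span Visit 3 have no counterpart.

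**Step 3: the trace.**

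| AE history | Treatment-emergent? | One record, period by start date | New dated record at each severity change |
|---|---|---|---|
| (a) Starts between Visit 2 and Visit 3 dosing, worsens after Visit 3 dosing | Yes, by the onset limb | *Before Visit 3*, possibly at its worst grade; nothing in the later period | Worsening falls in *During or After Visit 3* at the right grade |
| (b) Starts before the Visit 2 dose, worsens only after Visit 3 dosing | Yes, by the worsening limb | Period not defined; start date would put it before Visit 3 | *During or After Visit 3* |
| (c) Starts after Visit 3 dosing | Yes, by the onset limb | *During or After Visit 3* | Same |

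For example, a mild headache starts on Day 5, is still present at Visit 3 and becomes severe after the dose. It is already treatment-emergent by onset, so the worsening limb never comes into play. What is missing is a second anchor at Visit 3.

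**Step 4: direction.** Randomisation takes place at Visit 3, so AEs ongoing at dosing are balanced between arms in expectation. The same rule applies to both arms. Background worsening is lost about equally, and only an excess caused by PH94B would be understated.

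**Step 5: scale, under assumptions only.** The documents give no rates. Assume that 3 to 10% of the 104 subjects in an arm have an AE ongoing at Visit 3 and that 10 to 20% of those worsen:
- Low: 104 × 0.03 × 0.10 = 0.3 subjects (0.3%).
- High: 104 × 0.10 × 0.20 = 2.1 subjects (2.0%).

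This is the gross loss in one arm. The loss in the difference between arms is smaller. With 10% ongoing in both arms, 20% worsening on PH94B and 10% on placebo, it is 104 × 0.10 × (0.20 − 0.10) = 1.0 subject, or 1 percentage point. With equal worsening it is zero.

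**The case against.** The strongest reply is that the SAP does not prescribe the misplacement. A reader might infer that events are assigned to periods by onset, that the worst grade is carried back to the period of onset, and that worsening after PH94B is thereby credited to placebo. The documents do not go that far:

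- **Onset.** The stated criterion is time of occurrence. Onset is an inference, though a well-supported one (Step 2). This part of the reply stands as a limit on wording, not as a defence of the rule.
- **Worst grade.** The severity sentence selects among a subject's events. It does not say that one event takes its lifetime maximum back to an earlier period. Nor does it say that severity is limited to the period: the per-period sentence concerns counting subjects once. The point is open either way.
- **Recording.** If each severity change is a separate dated record, the worsening lands in the right period and the problem does not arise. Protocol 11.2 is compatible with that. For conditions present at screening, both documents say that later deterioration is recorded as an AE, which may give it its own date. Neither text settles AEs that arise between Visits 2 and 3.
- **Arms.** Events are also classified by Visit 3 group. A PH94B subject's event stays in the PH94B column of the earlier period and does not move to the placebo arm.
- **Consequence.** Safety analysis is descriptive, and AE listings flag treatment-emergent events. Start and stop dates are collected, so events that span Visit 3 can be found by hand.

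What survives is that no stated limb brings post-Visit 3 worsening into the later period. The outcome therefore rests on an eCRF convention and a programming choice that the plan does not fix.

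**Conclusion.** The gap is real and modest. Both limbs of the definition run from the Visit 2 placebo, while the tables are split at the randomised dose. An AE that starts before Visit 3 dosing and worsens after it has no limb that puts it in *During or After Visit 3 Dosing*. Under the likely reading it may be shown in the earlier period, possibly at its worst grade. The randomised comparison would then lose such worsenings in both arms, and any drug-related excess would be understated.

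The conclusion assumes assignment by start date and one eCRF record per event, neither of which is stated. The size cannot be computed from the documents. About a week between doses makes it probably small, and the 0.3 to 2.1 subjects per arm shown above rest on assumed rates. A general downward bias in the PH94B rate, or a transfer of PH94B events to the placebo arm, would be too strong a conclusion. This is a cheap improvement.

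**What to change.** In SAP 9.1, define treatment emergence by period:

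- **Before Visit 3 Dosing:** onset, or an increase in severity or relationship, from Visit 2 dosing up to Visit 3 dosing.
- **During or After Visit 3 Dosing:** onset at or after Visit 3 dosing, or an AE already present whose severity or relationship increases at or after that dose, through Visit 4.

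Take maximum severity and relationship within each period, using the severity changes that Protocol 11.2 requires to be documented. State how those changes are recorded: a new dated record, or an update with a date of change.

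The cost is SAP wording and one derivation rule. No new assessments are needed, provided that the documented severity changes carry dates. The SAP cites protocol Version 3.0 and states that no interim analysis is planned, whereas Version 4.0 adds one, so a SAP revision could carry this change too. The downside is that a worsening event may be counted once in each period; a table footnote should say so.

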9.1.1. Adverse Events Leading to Withdrawal

A summary of incidence rates (frequencies and percentages) of TEAEs leading to discontinuation of study drug will be summarized by period (Before Visit 3 Dosing and During or After Visit 3 Dosing), treatment group and overall subjects, and by SOC and preferred term for the Safety Population. No inferential statistical tests will be performed.

A data listing of AEs leading to discontinuation of study drug will also be provided, displaying details of the event(s) captured on the eCRF.

9.1.2. Deaths and Serious Adverse Events

Any deaths that occur during the study will be listed. Serious AEs will be listed. Serious TEAEs and serious TEAEs related to IP will be tabulated by SOC and preferred term and presented by period (Before Visit 3 Dosing and During or After Visit 3 Dosing), treatment group, and overall subjects.

9.2. Clinical Laboratory Evaluations

Descriptive summaries of observed values and change from baseline values will be presented for continuous hematology, chemistry, and urinalysis results for each treatment group, subjects not randomized and overall subjects at each study visit. Categorical urinalysis results will be summarized using frequencies by treatment group, subjects not randomized and overall subjects and by study visit.

The number of subjects with clinical laboratory values categorized as below, within, or above normal ranges will be tabulated showing change from baseline (shift tables) for each clinical laboratory analyte by treatment group and overall subjects and by study visit.

Laboratory values that are outside the normal range will also be flagged in the data listings and presented with the corresponding normal ranges. Any out-of-range values that are identified by the investigator as being clinically significant will be listed as an adverse event.

For women only, pregnancy status will be determined by evaluation of urine pregnancy test. Data on pregnancy status will be listed by subjects. Subjects who are pregnant are excluded from the study. Subjects who become pregnant during the study will be discontinued.

9.3. Vital Signs

Descriptive summaries of observed values and changes from baseline will be calculated for systolic blood pressure (mmHg), diastolic blood pressure (mmHg), heart rate (beats/min), respiratory rate (breaths/min), and temperature (°C) by treatment group, subjects not randomized and overall subjects and by study visit.

The number of subjects with vital signs values categorized as below, within, or above normal ranges will be tabulated showing change from baseline (shift tables) for each parameter by visit by treatment group and overall.

9.4. 12-Lead Electrocardiograms

The number and percentage of subjects with normal and abnormal 12-lead ECG findings will be summarized for each treatment group, subjects not randomized and overall subjects at each study visit. Abnormal results will be grouped as clinically significant and not clinically significant.

Descriptive summaries for the observed results and change from baseline will be presented for 12-lead ECG measures of PR interval (msec), QRS interval (msec), and heart rate for each treatment group and overall subjects at each study visit. If triplicate reads are taken, the mean of the reads will serve as the observed value at the specific visit.

A comparison of QT and QTcF results will be presented. Summary statistics for baseline values at Visit 1 (Screening) and Visit 4 (Follow-Up) will be displayed by treatment group and overall subjects for QT interval (msec) and QT interval corrected for heart rate using Fridericia's formula (QTcF) (msec). In addition, the number and percent of subjects in each treatment group who experienced a change >30 msec or a change >60 msec will be presented.

